## 9.3 Sensitivity analysis

We will conduct additional “post-hoc” analyses in which we will adjust for additional pre-specified potential confounders (table 1 below). The pre-specified confounders will be included in the models even when no baseline imbalance exists. We have limited the inclusion of potential confounding variables to those that we surmise to be the most important based on the investigators’ assessment of clinical plausibility. This approach has been chosen since confounder selection strategies which are based on collected data, for example selecting confounders using preliminary statistical tests, result in models with poor statistical properties such as incorrect type I error rates. Those confounders that are highlighted as having a significant impact in the subgroup analyses will also be included in these analyses to assess the impact on the treatment effect.

Table 1:

Level	No.	Confounder
Patient	1	Age (years, continuous)
	2	Sex (Male/Female)

Site	3	Rural/Urban
------	---	-------------

Some workers leave the workforce temporarily to take up higher paying seasonal or temporary work, with the intention of returning to the factory workforce after several months away. These workers undergo rigorous performance testing before being permitted to re-join the factory workforce. As the reason for leaving the workforce temporarily is not related to reduced productivity, we feel it is important to include a sensitivity analysis of the primary outcome that takes seasonal and temporary work patterns into account. To this end, in addition to the pre-specified sensitivity analyses outlined above, we will conduct supplementary analyses of the primary outcome that will focus on participants who exited the factory to pursue other seasonal or temporary employment opportunities at the conclusion of the 18-month primary data collection period, but who return to their positions in the factory within a four-month period after the conclusion of primary data collection.

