## 4.5 Interventions

Eligible participants will be randomly assigned to Intervention or Control Groups (1:1). Intervention group participants will receive free reading glasses after undergoing a vision screening at the factories, which will mark the beginning of the assessment period. In addition to receiving free reading glasses, participants in the Intervention Group will be eligible for free replacement glasses in the event of loss or damage throughout the trial. Control group participants will receive free reading glasses at the end of the assessment period (18 months after the beginning of the assessment period). An interim analysis will be performed by the trial statistician. If the Trial Management Group (TSG) terminates the trial on the recommendation of the trial statistician, then Control Group participants will receive free reading glasses at trial closure. The trial will be investigator-masked, but not participant-masked, because the investigators do not feel provision of zero-power glasses to the control group is ethical. However, participants will have limited knowledge of the study hypothesis, limiting potential placebo effects.

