#### 4.8 Sample size & power

Previous retention trials in this setting have showed 18-20% of overall likelihood of attrition at 5 months follow-up, 50% overall likelihood of attrition at 12 months, 60% at 18 months, 70% at 24 months. Assuming a work retention rate of 50% at 1 year and 40% at 18 months in the Control group, we anticipate that our glasses intervention will increase retention by 20% in the Intervention group at 1 year (hazard of 0.8). Data analysis using a Cox proportional hazard model with 2-sided significance at the 5% level and 80% power yields a total sample size of 1,260 (630 in each group). No correction for attrition is required as attrition is the outcome and therefore no attrition from the sample is possible.

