### 10.3 Recruitment

Using administrative data at the enrolled factories, we will identify job leavers between the 2nd to 6th month, and 12th to 15th month, compare the lists with the enrolment list for PROSPER III, and create a random-ordered list of job leavers to invite into this sub-study. A research team member will attempt to contact each person via telephone on the list in sequence, making up to three calls before declaring them 'unreachable' and removing their name from the recruitment list. Since there are cases of workers rejoining the factory within a few months, the enumerator will administer a short call reading out the information sheet (Annex 10) which mentions the purpose of the call and to check if they are planning to rejoin. Those who are planning to rejoin the factory within the next 6 months would be excluded from the qualitative study. Those who do not intend to return to the factory would be eligible for the qualitative survey. These workers would be informed of their eligibility and would be read out the Information Sheet which provides the information regarding their rights as a participant of the study. If the worker agrees to participate in the interview, their oral consent will be obtained, and they will be administered the interview as per the interview instrument sheet.

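### The seasonal-exit analysis in SAP 9.3 counts only returns in the four months after month 18, so workers who leave and come back during the trial are not covered

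*SAP*

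**What the plan says.** SAP 9.3 explains that some workers leave for better-paid seasonal or temporary jobs and mean to return after some months. Because such departures are not put down to falling productivity, it wants a sensitivity analysis of the primary outcome that allows for them. The rule is: "we will conduct supplementary analyses of the primary outcome that will focus on participants who exited the factory" for such work at the conclusion of the 18-month data collection, but "who return to their positions in the factory within a four-month period after the conclusion of primary data collection".

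Four other places bear on this:

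- SAP 4.6.1 defines the endpoint as time from randomisation to loss of employment. It has no rule for a worker who leaves and rejoins.
- SAP 4.10.2 collects employment status daily and assesses it weekly over the 18 months.
- SAP 10.3 notes that "there are cases of workers rejoining the factory within a few months". It excludes from the qualitative interviews those who plan to rejoin within six months.
- SAP 4.5 states that "Control group participants will receive free reading glasses at the end of the assessment period", which is month 18.

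**The concern.** The aim concerns temporary absence, but the rule selects on position relative to the end of the trial. A worker who leaves in month 4 and is back in month 7 fits the rationale and is not covered. Under 4.6.1 that first exit is naturally read as an event, and nothing in 9.3 revisits it. If being away at month 18 is enough, a worker who left in month 4 and returned in month 20, after 16 months away, is covered.

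Two further problems come with the sentence. The return window begins when Controls are due glasses, so returns in months 18 to 22 may be affected by the end of the glasses contrast. SAP 9.3 also says that returners must pass performance testing, which near vision could plausibly influence. And the text names the workers of interest without saying whether their exits are recoded, censored or set aside. Taken literally, it restricts the analysis to a subset defined by the outcome, which does not sit with the intention-to-treat comparison in 7.1.

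What is at stake is whether the analysis can show dilution. As an illustration on assumed figures, if 10% of exits are temporary with hazard ratio 1 and the rest have 0.8, the overall ratio is about 0.9 × 0.8 + 0.1 × 1 = 0.82. At 20% it is about 0.84. An analysis that leaves most temporary exits counted as events cannot reveal this.

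**Working it through.** **Scale.** The SAP gives no figure for this analysis, so I first reproduced its sample size (4.8: hazard ratio 0.8, two-sided 5%, 80% power, 1:1). Schoenfeld events = 4 × (1.960 + 0.842)² / (ln 0.8)² = 630.5. Divided by an overall event probability of 0.5, this gives 1,261, against the stated 1,260.

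**Exit curve.** From 4.8, Control retention is S(5) = 0.80 (the 20% end of the 18–20% attrition range), S(12) = 0.50 and S(18) = 0.40. I took a constant hazard between these points and S(t)^0.8 in the Intervention arm. Expected exits by month 18 are 630 × (1 − 0.400) + 630 × (1 − 0.480) = about 705.

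**Assumptions.** Temporary exits are timed like all exits. Absence lasts D months; the SAP gives no figure, so I used 3 to 9.

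**Who is reached.** The exit condition has two readings:

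- Narrow: the worker left at about month 18, taken here as the last month.
- Broad: the worker is away at month 18, whenever he or she left. The exit must then fall between months 18 − D and min(18, 22 − D), which is never more than four months of exit dates.

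Worked example, D = 4, exits in months 14 to 18:

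- Control: S(14) = 0.50 × (0.40/0.50)^(2/6) = 0.464, so (0.464 − 0.400)/0.600 = 10.7%.
- Intervention: (0.541 − 0.480)/0.520 = 11.7%.
- Pooled: 630 × (0.0642 + 0.0607) = 78.7 of 705, or 11.2%.
- Linear interpolation for Control gives nearly the same: F(14) = 0.533 and (0.600 − 0.533)/0.600 = 11.1%.

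| Reading | Exit months reached | Control | Intervention | Pooled exits (of 705) | Reached | Missed |
|---|---|---|---|---|---|---|
| Narrow | 17–18 | 2.5% | 2.8% | 19 | 2.6% | 97% |
| Broad, D = 3 | 15–18 | 7.9% | 8.6% | 58 | 8.2% | 92% |
| Broad, D = 4 | 14–18 | 10.7% | 11.7% | 79 | 11.2% | 89% |
| Broad, D = 6 | 12–16 | 11.5% | 12.4% | 84 | 11.9% | 88% |
| Broad, D = 9 | 9–13 | 21.6% | 22.6% | 156 | 22.1% | 78% |

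The counts are all exits in the window. Under the timing assumption, the percentages carry over to temporary exits.

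Most of what is missed is return before month 18. In the Control arm this is 92% of exits at D = 3 and 65% at D = 9; at D = 9 a further 14% are still away at month 22. Taking S(5) = 0.82 instead moves the Control figure for D = 9 from 21.6% to 22.7% and leaves the other rows unchanged.

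**The case against.** The strongest reply is that the sentence is loose rather than wrong. Being away at month 18, whenever the worker left, is a fair reading of the exit condition. A reader might infer that only workers who leave around month 18 are covered, but the text does not force that. The second reading widens the exit dates; it does not move the return window, so in-trial returners stay outside.

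The percentages describe all exits. The SAP gives neither the number nor the timing of temporary ones, and seasonal work may cluster, which could move the shares either way. This stands, and the figures are conditional for that reason.

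A reader might also infer that Controls who return in months 18 to 22 already have glasses. The SAP schedules glasses for month 18 but does not say whether a Control who is away then gets them before or after coming back. An effect on returns is possible, not shown.

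Nor can the plan be charged both with recoding too few exits and with analysing exiters alone. It states neither; the defect is that no handling rule is given.

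Finally, any dilution arises in the primary endpoint, which has no re-entry rule, and this analysis is only supplementary. That is correct and limits the weight of the point.

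**Conclusion.** The point holds in a limited form. On either reading of the exit condition, the analysis in 9.3 omits workers who leave and return within the 18 months. These are workers it was meant to take into account, and the data to identify them are already collected. If temporary exits are timed like all exits on the 4.8 curve, it reaches about 3% of them on the narrow reading and about 8% to 22% on the broad one for absences of 3 to 9 months. Most are therefore missed. To say that nearly all are missed would fit only the narrow reading.

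The overlap of the return window with the date when Controls are due glasses is a risk that the plan does not guard against. The absent handling rule is a defect in itself. None of this bears on the primary inference, which 9.1 rests on the adjusted analysis. The point should be put right but is not critical.

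**What to change.** Replace the final sentence of 9.3 with a rule tied to each worker's own exit:

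- Repeat the primary Cox analysis in all randomised workers, by allocated arm, with the same rule in both arms.
- An exit at any time from randomisation to month 18 is not an event if HR records show re-employment within a fixed window of that worker's exit date. Use four months, and also six months to match the rejoining horizon in 10.3.
- Follow-up continues after return. A later exit without return inside the window counts as the event.
- Where a reason for leaving is recorded, also report the result with the rule limited to seasonal or temporary work, since the rationale in 9.3 rests on the reason.
- For exits whose window runs past month 18 (after month 14 for four months, after month 12 for six), report results with and without returns after month 18.

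Absences longer than six months would still count as events, but under a stated rule that is the same in both arms.

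The cost is SAP wording and a little extra analysis. The four-month version needs HR records to month 22, which the present text already implies. The six-month version needs them to month 24, or can be truncated at month 22.

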#### **9.4 Significance levels and adjustment of p-values for multiplicity**

For the primary and secondary outcome, including subgroup analyses, a 95% confidence interval will be calculated.

#### **9.5 Procedure for accounting for missing, unused, and spurious data**

Missing data will be described, for example, by presenting the number and percentage of individuals in the missing category. All data collected on data collection forms will be used, since only essential data items will be collected.

#### **9.6 Exclusion of data**

Before data are locked for statistical analysis, a blinded review of all data will take place. Any decision to exclude a subject or single observation from the statistical analysis is the joint responsibility of the PROSPER III trial statistician, the international trial manager and the Chief Investigator. Exclusion of data from analyses will be used restrictively and normally no data should be excluded from the full analysis set. The subjects or observations to be excluded, and the reasons for their exclusion will be documented and signed by those responsible before database lock. The subjects and observations excluded from analysis sets, and the reason for this, will be described in the clinical trial report. Any observation excluded from the analysis database will be documented before database lock with the reason for exclusion provided.

#### **9.7 Statistical software employed**

Stata, version 18

### **10. QUALITATIVE SUB-STUDY**

One of the hypotheses being tested in PROSPER III is providing glasses to correct presbyopia in sewing operators in India can reduce attrition. The RCT will collect data comparing the attrition rates of Intervention and Control group subjects; however, this will not explain why

sewing operators have left their jobs, and the role that vision plays in that decision. This qualitative sub-study will provide this additional information.

### 10.1 Research Design

The descriptive qualitative study design is frequently used in mixed methods research because its outcome – a straightforward report on methods and findings close to participants' own voices – makes it relatively easy to integrate quantitative and qualitative findings. Furthermore, our aim is to highlight the voice of sew-ers who have left Shahi during the study rather than develop a theoretical model or explore pre-determined factors thought to affect their decisions.

### 10.2 Sample and Sample Size

The sampling frame or set of potential participants will be all PROSPER III subjects who leave the employ of Shahi before the end of the study. A criterion-based purposive sampling framework will be used for selecting the respondents for interviews to expand the range of variation in responses while allowing for identifying similarities and differences. The criteria used to create the strata for the sub sample would be:

- Early leavers vs late leavers (with relation to the start of the study)
- Treatment status
- Power of glasses (Low - Visual acuity <=N6.3; Moderate >=N8)

In a descriptive qualitative study, approximately 20 participants can provide enough data to reach informational redundancy or data saturation (the point when no new information emerges from the last round of data collected) and theoretical saturation (the point when the researchers identify themes or categories with enough data to support their interpretations of each one). If some participants do not provide rich data, then additional persons must be recruited to reach saturation. Because we will be selecting participants from each of the 8 categories based on the criterion strata's, we will increase the total sample size to 40 persons, planning for an additional five interviews if needed. The sample for each category would range between 3-6 depending upon the quality of response we get. The sampling framework for selecting the participants is described in table 2.

Table 2:

CRITERIA	CATEGORIES							
When left trial	Early (2rd – 6th month)				Later (12th - 15th month)			
Treatment status	Control Group		Intervention Group		Control Group		Intervention Group	
Prescription strength	low	moderat e	low	moderat e	low	moderat e	low	moderat e

Sample size per category	3-6	3-6	3-6	3-6	3-6	3-6	3-6	3-6
--------------------------	-----	-----	-----	-----	-----	-----	-----	-----

Administrative data from Shahi indicate that about 20% of their workers leave after 5 months of employment, 50% after 12 months and 60% after 18 months. Assuming that the attrition rate for sew-ers is similar, we will have a large enough sampling frame to identify and enroll 40-45 participants.

### 10.3 Recruitment

Using administrative data at the enrolled factories, we will identify job leavers between the 2nd to 6th month, and 12th to 15th month, compare the lists with the enrolment list for PROSPER III, and create a random-ordered list of job leavers to invite into this sub-study. A research team member will attempt to contact each person via telephone on the list in sequence, making up to three calls before declaring them 'unreachable' and removing their name from the recruitment list. Since there are cases of workers rejoining the factory within a few months, the enumerator will administer a short call reading out the information sheet (Annex 10) which mentions the purpose of the call and to check if they are planning to rejoin. Those who are planning to rejoin the factory within the next 6 months would be excluded from the qualitative study. Those who do not intend to return to the factory would be eligible for the qualitative survey. These workers would be informed of their eligibility and would be read out the Information Sheet which provides the information regarding their rights as a participant of the study. If the worker agrees to participate in the interview, their oral consent will be obtained, and they will be administered the interview as per the interview instrument sheet.

### 10.4 Time Period

Since the study seeks to explore the reasons behind workers leaving the factory and if vision issues are one of them, it is crucial to explore if workers leaving at the beginning of the study were more likely to be suffering from vision problems and the impact they had on their work, as compared to those who left later into the study. For this purpose the study would be conducted in two phases, the first phase would follow up on workers who have left the factory between 2- 6 months. The second phase of interviews would be conducted for workers who have left the factory between the 12-15th month.

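### The interview quotas on near acuity approximately set the early and late leavers' acuity mix, so the sub-study cannot show whether workers with worse measured near vision leave earlier

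*SAP*

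**What the plan says.** Section 10.4 (Time Period) states the question: "it is crucial to explore if workers leaving at the beginning of the study were more likely to be suffering from vision problems", together with the impact on their work, relative to those who left later. It then links the design to that question: "For this purpose the study would be conducted in two phases". One phase covers leavers in months 2-6 and the other covers months 12-15.

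Section 10.2 (Sample and Sample Size) sets the selection: "A criterion-based purposive sampling framework will be used for selecting the respondents for interviews to expand the range of variation in responses". The strata are leaving window, allocated arm and a vision criterion, "Power of glasses (Low - Visual acuity <=N6.3; Moderate >=N8". On numbers it says "The sample for each category would range between 3-6 depending upon the quality of response we get", with 40 interviews planned and five more if needed. Table 2 shows the same 3-6 target in all eight cells.

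Section 10.3 calls leavers from a randomly ordered list. Section 10.6.5 charts categories by frequency count, and 10.7 promises a rank-ordered list of reasons and a report on the role of poor near vision in job leaving. Section 8.2 records uncorrected near acuity and power of near correction at baseline for the whole trial.

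**The concern.** Whether one group was more likely than another to have a vision problem depends on how common the problem is in each group. A sample chosen to contain set numbers of each acuity level in each group carries no information on that for measured acuity. If poor near vision does drive early exit, and more workers with moderate loss leave in months 2-6 than in months 12-15, the interview sample will still look much the same in both windows. Frequency counts by window would inherit the fixed mix. A flat pattern could then be taken as a sign that near vision is unrelated to early leaving, when the sampling table produced it. An uneven pattern could be taken as a signal, when it arose because some cells were extended to get fuller responses.

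Nothing else in the SAP fills the gap. The degree-of-presbyopia subgroup in 9.2 tests whether the treatment effect varies with severity, not when workers leave. No section tabulates acuity by time of leaving.

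**Working it through.** **1. The plan's own sample size.** Two windows × two arms × two acuity levels = 8 cells. At 3-6 per cell the total lies between 8 × 3 = 24 and 8 × 6 = 48, which contains the stated 40 and 45. At 40 there are 40/8 = 5 per cell. The plan's figures are consistent.

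**2. Acuity mix per window.** At 5 per cell, each window has 2 arms × 5 = 10 low and 10 moderate. The moderate share is 10/20 = 50% early and 50% late, a difference of 0.

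**3. How far the range lets it move.** Within one window the moderate share is lowest at 6/(6 + 12) = 33% and highest at 12/(12 + 6) = 67%. Going through all cell counts of 3-6 with a total of 40-45, the largest difference between windows is 12/18 − 10/22 = 66.7% − 45.5% = 21 points. Section 10.2 ties that freedom to response quality, not to who left.

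**4. Contrast with unrestricted sampling.** Assume, for illustration only, that 70% of early and 30% of late leavers have moderate loss. A random sample of 20 leavers per window would show +40 points on average. The quota sample at 5 per cell shows 0. The random call order in 10.3 does not change this, because the acuity cells still have to be filled.

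**5. How many leavers the trial itself will have.** Inputs: Control retention 80%, 50% and 40% at 5, 12 and 18 months, hazard ratio 0.8 and 630 per arm (4.8; attrition also in 10.2). Assumption: cumulative hazard H(t) = −ln S(t) is linear between those times, so H(5) = 0.223, H(12) = 0.693 and H(18) = 0.916. Intervention retention is exp(−0.8 H).

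- Elapsed months 2 to 6: Control 630 × (0.9146 − 0.7480) = 105; Intervention 630 × (0.9311 − 0.7928) = 87; total 192.
- Elapsed months 12 to 15: Control 630 × (0.5000 − 0.4472) = 33; Intervention 630 × (0.5743 − 0.5253) = 31; total 64.
- Counting from the start of month 2 and of month 12 (elapsed 1-6 and 11-15): Control 131 and 55, Intervention 108 and 51; totals 240 and 106 after rounding.
- By month 18: 630 × 0.600 + 630 × 0.5196 = 378 + 327 = 705.

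**6. What a direct comparison of leavers could detect.** Assume true moderate shares of 65% early and 45% late (not in the SAP). Two-proportion z test, two-sided 5%: power = Φ[(0.20 − 1.96 SE₀)/SE₁], with SE₀ from the pooled proportion and SE₁ from the separate ones. For 192 v 64, the pooled proportion is 0.60, SE₀ = 0.0707 and SE₁ = 0.0711, so power = Φ(0.864) = 81%.

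| Leavers compared | Early v late | Power |
|---|---|---|
| Both arms, narrow count | 192 v 64 | 81% |
| Both arms, wide count | 240 v 106 | 94% |
| Control only | 105 v 33 to 131 v 55 | 53% to 72% |
| Intervention only | 87 v 31 to 108 v 51 | 50% to 67% |

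The pooled comparison is reasonably informative. The comparison within one arm is not, and can only be descriptive.

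**The case against.** The strongest reply is that this is a descriptive qualitative study. Purposive quotas are standard for it, 10.4 speaks of exploring, and the analysis steps in 10.6 contain no table, test or weighting by leaving window. None of the outcomes in 10.7 is an early-versus-late contrast. Every participant has near acuity of N6.3 or worse (4.4.1), so the vision problems in 10.4 can fairly be read as difficulty experienced at work, and that can differ between windows within an acuity stratum. The moderate stratum is also open-ended, so severity within it can vary.

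Most of this stands, and it rules out three stronger readings that a reader might draw.

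- That the sub-study cannot tell early from late leavers at all. The limit applies only to the measured acuity stratum. Reported difficulty, its impact and reasons for leaving remain open to exploration.
- That the quotas also fix who has corrected vision. They fix allocation. Section 5.2.2 allows that Intervention workers may not receive glasses and that Control workers may buy their own, and wear is measured separately (section 6).
- That a planned significance test will fail. The SAP plans no such test on the interviews.

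The reply does not remove the conflict itself. Section 10.4 asks which group was more likely to have the problem and gives that as the purpose of the two phases, while 10.2 selects on a measure of that problem with identical targets in both windows.

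**Conclusion.** The point holds in a limited form. The early and late samples' mix of measured near acuity is set approximately by the quotas: 10 and 10 per window at 5 per cell, and at most about 21 points apart at 40-45 interviews. It cannot show whether workers with worse near vision leave earlier. This follows from Table 2 alone and needs no assumption about the true mix.

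The leaver counts rest on the plan's attrition figures, hazard ratio and interpolation between time points. The power figures also rest on an assumed 65% v 45% difference. Baseline acuity and lens power answer the measured-vision part of the question. They do not show what a worker experienced at the time of leaving, which remains the task of the interviews. No randomised primary or secondary comparison is affected, so this is a modest correction of one stated aim and not a fault in the sub-study as a whole.

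**What to change.** In 10.4, answer the early-versus-late question descriptively from trial data on all leavers. Tabulate baseline unaided near acuity and power of near correction (already recorded under 8.2) by leaving time, including the two interview windows, pooled and by arm. Label the by-arm tables descriptive.

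In 10.4 and 10.7, state that the interviews describe experience, impact on work and reasons for leaving, and are not used to say that one group of leavers was more likely to have vision problems. If interview frequencies are nevertheless compared across windows, weight each cell to its share of actual leavers.

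A Cox model with baseline vision by time is optional. If it is fitted, mark it exploratory under section 12.

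Cost: one extra table on data already collected, and a few sentences. No new interviews are needed and the quotas stay as they are. The downside is that the interviews can no longer be cited for an early-late frequency statement.
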